## **1.0 BACKGROUND AND RATIONALE**

### **1.1 Study Synopsis**

The parotids have not been historically considered an organ at risk / avoidance structure and are not routinely delineated for whole brain radiation (WBRT) planning, despite receiving incidental dose [1] using standard fields. For this reason, we evaluated patient reported xerostomia in an ongoing prospective observational trial (LCCC 1540: Prospective Evaluation of Patient Reported Xerostomia After Whole Brain Radiation). At an interim analysis of LCCC 1540 with accrual at 90% of the goal, we found a clinically-meaningful rate of xerostomia following routine WBRT. Furthermore, the incidence/severity appeared to be related to parotid dose. The goal of this follow-up study is to investigate whether parotid sparing WBRT can reduce or prevent patient reported xerostomia. The study design will principally be a prospective randomized trial where patients are randomized to receive parotid sparing WBRT vs. standard WBRT where the parotids are not avoided. We will evaluate the xerostomia scores (using the University of Michigan Xerostomia Questionnaire [2]) of patients treated in each arm. Patients who refuse randomization will be offered enrollment in an observational arm to follow their symptoms of xerostomia for secondary analysis. This will be a multi-site study, with patients also enrolling at High Point Regional Health, High Point, North Carolina, as well as possibly other sites and institutions. We anticipate a total accrual of approximately 90 patients (45 in each interventional arm) with a goal of 62 evaluable patients reaching the primary 1 month post-RT endpoint.

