### **2.2 Secondary Objectives**

Secondary objective #1: To assess whether the use of parotid sparing WBRT fields results in an increase in marginal tumor relapses in the region of the blocked parotid glands *in randomized patients*.

Secondary objective #2: To assess whether the use of parotid sparing WBRT fields results in decreased xerostomia *in all patients, including randomized patients and patients who refused randomization but consented for the observational arm*.

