### **2.4 Endpoints**

Primary endpoint: The primary endpoint will be the proportion of patients experiencing clinically significant xerostomia (defined as a  $\geq 15$  point increase in composite University of Michigan Xerostomia Questionnaire score [2]) *in randomized patients* from baseline to 1 month post-treatment.

Secondary endpoint #1: Freedom from marginal relapse, including CNS relapse in the inferior brain (defined as within 1 cm of the block edge overlying the blocked parotids), and the rate of upper cervical spine relapse (defined as relapses in the C1 or C2 vertebrae).

Secondary endpoint #2: Xerostomia (defined as a  $\geq 15$  point increase) at 1 month based on the use of standard vs. parotid sparing fields *in all patients, including randomized and non-randomized patients*.

Exploratory endpoint: [REDACTED]

[REDACTED]

Exploratory endpoint #2: [REDACTED]

[REDACTED].

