### **4.3 Study Details**

This is primarily a two-arm, single-blind, randomized study of parotid sparing WBRT, with a third observational arm of patients who were identified after radiation had already started or who refused randomization but were willing to be followed for quality of life assessment. The primary purpose of this study is to compare the proportion of patients experiencing significant xerostomia in patients randomized to parotid sparing vs. standard WBRT. Patients receiving WBRT often receive treatment in urgent situations, making pre-treatment randomization logistically challenging. Therefore, the observational arm serves to increase the number of eligible patients and allows for comparison of xerostomia in all patients receiving parotid sparing vs. standard WBRT, but who were unable to be approached in time for randomization. Patients enrolling on the randomization arms will be consented and enrolled prior to treatment. Patients enrolling on the observational arm may enroll up to 5 days after initiation of treatment. Post-treatment surveys will be collected up to 6 months post-RT. We therefore anticipate that patients' active participation will last approximately 6 months. Chart abstraction will take place for up to 1 year post-RT for assessment of secondary endpoint #1: freedom from marginal relapse.

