#### 4.3.7 Treatment Planning and Delivery – Arm C: Observational arm (WBRT protocol not specified)

Patients who decline randomization but consent to the observational arm will receive WBRT without the use of the above treatment planning guidelines. WBRT will be delivered using standard or parotid sparing fields, per treating physician preference. Patients may also enroll on this arm after initiation of WBRT, as long as the baseline questionnaire is completed within 5 days of initiation of treatment. These patients will complete the protocol-specified study assessments at the same time points as randomized patients.

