#### 4.3.9 Main Study Assessment: Xerostomia Questionnaire

Patients in this study will be asked to complete the Xerostomia Questionnaire and two additional supplemental survey questions at baseline (prior to radiation in randomized patients and within 5

days of radiation initiation in patients refusing randomization but consenting for the observation arm), at the end of radiation (on or within 5 days after the final day of radiation), then at two weeks (+/- 5 days) and one, three, and six months (+/- 7 days) after radiation completion, for a total of six planned surveys. This survey may be administered by phone or by email, vs. in person if the patient has an appointment at the appropriate time point necessary for clinical follow-up. This survey also acts as the screening questionnaire completed by patients prior to enrollment, and counts as the baseline questionnaire for those consenting to enrollment.

The full survey (see appendix) will consist of the validated University of Michigan Xerostomia Questionnaire (questions 1-8) and two additional questions related to dry mouth, (questions 9-10). Questions 1-8 will be answered on a Likert scale ranging from 0 (least bothersome) to 10 (most bothersome), summed, and linearly converted to a scale from 0-100. Questions 9-10 will be answered on a Likert scale with four responses: Not at all, a little, quite a bit, and very much. Questions 9-10 are designed to quantify the overall importance of dry mouth symptoms to each patient, and were adapted from the validated EORTC QLQ-H&N35 head and neck specific questionnaire [17].

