### **7.3 Data Analysis Plans**

The primary data analysis plan is to compare the proportion of patients in each randomization arm experiencing a  $\geq 15$  point xerostomia score increase between baseline and 1 month, with the use of a two group chi-square test. As sample size allows, linear mixed effects models will be explored to evaluate changes over time including all repeated measurements. It is anticipated that a significant number of enrolled patients will be unable to complete the 3 month (estimated 40% response rate) and 6 month (estimated 20% response rate) post-radiation questionnaires due to disease morbidity and mortality, so modeling may be limited to the earlier time points. In such a

scenario with significant patient dropout, separate analyses will be performed for patients with vs. without long term follow up.

Descriptive statistics will be provided for all scores at all time-points and to summarize the patient population. Secondary data analyses will estimate the time to marginal relapse (defined as within 1 cm of the block edge overlying the blocked parotids) and the time to upper cervical spine relapse (defined as relapses in the C1 or C2 vertebrae) in each randomization arm using the Kaplan Meier method. A log rank test will be used to compare these time to event outcomes. Furthermore, the above analyses exploring xerostomia will also be conducted in all patients (including those who refused randomization but consented for the observational arm).

A linear regression model will be used to further explore the dosimetric relationship between parotid dose and xerostomia, to supplement data from LCCC 1540.

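### Secondary endpoint #2 pools randomized and Arm C patients by field used, with no cohort term or covariate, although Arm C fields are physician-chosen and some Arm C baselines may fall after radiation has started

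*Combined protocol and SAP*

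**What the plan says.** Section 2.4 defines secondary endpoint #2 as xerostomia "at 1 month based on the use of standard vs. parotid sparing fields", assessed "in all patients, including randomized and non-randomized patients". For the analysis, Section 7.3 says only that "the above analyses exploring xerostomia will also be conducted in all patients". The preceding xerostomia analyses are a two-group chi-square test and, if numbers permit, linear mixed models. Section 7.3 names no cohort indicator, stratum or covariate for the pooled set, and no by-field estimate within Arm C.

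Arm C differs from the randomized arms in two ways:

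- **Field.** Section 4.3.7 says that "WBRT will be delivered using standard or parotid sparing fields, per treating physician preference", without the planning guidelines of the randomized arms.
- **Baseline.** Sections 3.1.2, 3.1.5, 4.3.7 and 5.1 (note 1) allow the Arm C questionnaire up to 5 days after radiation starts. Randomized patients complete it beforehand.

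Section 4.3.10 records ECOG status and, explicitly to assess possible confounding of dry mouth, medication use. Section 7.3 uses none of these data.

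Descriptions of the added patients vary. Section 2.2 speaks of "patients who refused randomization but consented for the observational arm", and the parenthesis in Section 7.3 is similar. Section 4.3 also places patients identified after radiation start in Arm C and describes a comparison in those "who were unable to be approached in time for randomization".

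**The concern.** Randomization protects the comparison of Arm A with Arm B. Adding Arm C and comparing everyone by field gives up part of that protection in three ways.

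1. **Cohort differences.** If Arm C has a different underlying risk and an unequal mix of fields, a crude comparison turns the cohort difference into an apparent field effect.
2. **Selection by field.** Section 1.3 describes physicians as divided: some already spare the parotids off trial, while others keep standard fields. Field choice may therefore track physician, site or patient.
3. **Baseline timing.** Courses run 10 to 15 fractions (Section 3.1.1). Assuming one fraction a day, a baseline at day 5 could follow roughly 5/15 to 5/10 of the course. Any dryness already present is subtracted from the 1-month change. The schema note in Section 4.1 expects many patients to be identified after treatment begins, so this need not be rare.

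At stake is the interpretation of a listed secondary endpoint. If the pooled result differed from the randomized one, no planned estimate would show why.

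**Working it through.** **The plan's own figures.** With 42% against 14%, one-sided alpha 0.05 and 80% power (Section 7.2), the mean rate is 0.28 and

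n = [1.645 × √(2 × 0.28 × 0.72) + 0.842 × √(0.42 × 0.58 + 0.14 × 0.86)]² / 0.28² = 30.7, so 31 per group (power 80.3%).

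Enrollment: 62 / 0.70 = 88.6, so 89, against 90 planned. Both reproduce, but they concern only the randomized comparison. No size, field mix or risk is given for Arm C, so what follows is illustration.

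**Assumptions.** 31 + 31 evaluable randomized patients; 30 to 60 evaluable Arm C patients, 20% to 80% of them on standard fields; normal change scores with SD 26 (Section 7.1), set to give 42% and 14% at the 15-point cut. If scores have already risen by s points at a late baseline, the rate becomes P(Z ≥ z + s/26), with z = 0.202 (standard) or 1.080 (sparing):

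| Rise at late baseline | Standard | Sparing |
|---|---|---|
| 0 | 0.420 | 0.140 |
| 5 | 0.347 | 0.102 |
| 10 | 0.279 | 0.071 |

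Differences below are standard minus sparing.

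**Timing, no true effect, all of Arm C late.** Take 60 in Arm C, 80% standard, rise 10:
- Standard: (31 × 0.42 + 48 × 0.279) / 79 = 0.334
- Sparing: (31 × 0.42 + 12 × 0.279) / 43 = 0.381
- Crude difference: −0.046

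Over rises of 5 to 10 and all three Arm C sizes, an 80:20 split gives 2.0 to 4.6 points in either direction, 1.0 to 2.3 if half are late, and 0 at 50:50. The crude standard error is 8.6 to 10.4 points. Stratifying by cohort gives 0 throughout.

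**Timing, true 28-point effect.** Same example:
- Crude: (31 × 0.42 + 48 × 0.279) / 79 − (31 × 0.14 + 12 × 0.071) / 43 = 0.213
- Mantel-Haenszel weights: 31 × 31 / 62 = 15.5 (randomized) and 48 × 12 / 60 = 9.6 (Arm C)
- Stratified: (15.5 × 0.280 + 9.6 × 0.207) / 25.1 = 0.252

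| Arm C on standard fields | Crude | Stratified |
|---|---|---|
| 20% | 0.282–0.287 | 0.252–0.272 |
| 50% | 0.244–0.269 | 0.244–0.269 |
| 80% | 0.213–0.254 | 0.252–0.272 |

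Stratifying is closer to 0.28 only at 80% standard. What remains is attenuation within Arm C, which a cohort term cannot remove.

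**Selection only, no field effect.** Arm C risk 0.32 on sparing and 0.42 on standard fields; 60 patients, 20% standard:
- Crude: 0.42 − (31 × 0.42 + 48 × 0.32) / 79 = 0.061
- Stratified: 9.6 × 0.10 / 25.1 = 0.038

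Over the grid, crude is 0.016–0.061 and stratified 0.024–0.049. At 80% standard the stratified value is further from zero (0.024–0.038 against 0.016–0.028).

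**False-positive rate.** Simulation with 200,000 replicates: no field effect, 42% in both randomized arms, 20 to 62 Arm C patients, 25% to 75% sparing, one-sided 5% test:

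| Arm C risk (sparing / standard) | Pooled | Stratified |
|---|---|---|
| 30% / 30% | 2.4–9.9% | 4.6–5.3% |
| 32% / 42% | 6.5–16.5% | 6.8–14.2% |
| 32% / 52% | 10.8–29.4% | 9.4–29.2% |

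**Check on the model.** The mean of 17.8 and SD of 26.0 in Section 7.1 imply P(Z ≥ (15 − 17.8)/26) = 54% under normality, not 42%. Re-anchored at 54% against 26%, the crude estimate with equal shifts is 0.218–0.304, and the no-effect bias reaches 0.050 in either direction. The pattern is similar.

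**The case against.** **Materiality.** Every Arm C input is assumed. Timing bias with no true effect is below one standard error, and a 10-point rise within 5 days would be more than half the 17.8-point mean change seen at 1 month. This stands as a limit on any claim about size. It does not defend the method, since such bias does not shrink as patients are added.

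**Selection on patient risk is conjecture.** Section 1.3 describes a split between physicians, and no passage ties field choice to xerostomia risk. This stands, and if choice follows physician or site, the recorded covariates will not capture it. The plan still offers no protection.

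**Stratification can do worse.** It can, as shown at 20% standard under the effect and at 80% standard under selection. A cohort term is therefore only part of the remedy.

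**Arm C may be reported separately anyway.** Section 4.3 can be read that way, and Section 7.3 promises descriptive statistics for all scores. Neither specifies an Arm C estimate by field.

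**Who is pooled.** A reader might infer that the sections contradict each other, because Sections 2.2 and 7.3 name only refusers. The documents do not support that: Sections 2.2, 2.4 and 7.3 all say all patients and then use a form of including, which excludes nobody. The wording is incomplete.

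**Refusers' baselines.** A reader might also infer that late baselines affect refusers as much as others, because Section 4.3.9 allows a questionnaire within 5 "days of radiation initiation in patients refusing randomization but consenting for the observation arm". But Section 4.3.1 has refusers identified before radiation and screened before enrollment is offered, so their baseline would ordinarily come first. Late baselines arise mainly in late-identified patients.

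**Conclusion.** The point holds for secondary endpoint #2 and should be fixed. As written, the pooled analysis is open to cohort imbalance, to selection by field and, for late-identified patients, to baseline timing. The documents settle neither size nor direction; the figures above rest on assumed Arm C size, field mix, risk and early score change.

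Two stronger conclusions are not supported. The primary result is not compromised, because it uses randomized patients only and is analyzed on its own. Nor do the documents show that the pooled estimate will be biased in a particular direction: in some scenarios the crude estimate lies close to the truth.

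**What to change.** In Sections 2.2, 2.4 and 7.3:

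1. Report the Arm C estimate by field separately, beside the randomized estimate.
2. Combine the two only in an analysis stratified by cohort (Mantel-Haenszel, or logistic regression with a cohort term), with one or two pre-specified covariates already recorded, such as ECOG status and baseline anticholinergic or narcotic use. State that the cohort term deals with differences between cohorts only, and that these covariates do not capture choice by physician or site. Whether to adjust for baseline score can be left to the statistician.
3. Add a sensitivity analysis limited to patients whose baseline preceded the first fraction. First confirm that this timing is captured: Sections 3.1.5 and 8.3 imply it, but it is not listed as a data item.
4. Label the combined result partly non-randomized.
5. Align the population wording in Sections 2.2 and 7.3 with Sections 2.4 and 4.3.
6. State how an Arm C plan is classified as standard or sparing. Section 4.3.7 applies no planning guidelines, and Section 4.3.10 describes parotid delineation only for randomized patients.

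Cost: mostly analysis wording, since the covariates are collected under Section 5.1; the classification rule and the timing check need some work. Stratified standard errors are up to about 8% larger, and about equal at a 50:50 field mix. Under the planned effect the pooled set would hold only about 21 to 39 events, so the covariate list must stay short. The sensitivity analysis has a standard error of about 9 to 10 points if 15 to 30 Arm C patients remain, against √[(0.42 × 0.58 + 0.14 × 0.86)/31] = 10.8 points for the randomized patients alone.

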#### **7.4 Data Management/Audit**

The University of North Carolina will serve as the coordinating center for this trial. All data will be collected, entered, and maintained in a database on secure servers at the University of North Carolina at Chapel Hill. Questionnaires will be collected via Qualtrics and each site will be responsible for ensuring all questionnaires are entered into Qualtrics. Outside sites, including the University of Michigan and Wake Forest University (High Point Regional Health), will send any other data via secure email to the University of North Carolina at Chapel Hill. All data will be pooled at UNC where personnel there will coordinate and manage data for quality control assurance and integrity. Data analysis will take place at UNC as well. Accrual data will be collected and entered into OnCore®. As an investigator-initiated study, this trial will also be audited by the Lineberger Cancer Center audit committee.

### **8.0 STUDY MANAGEMENT**

#### **8.1 Institutional Review Board (IRB) Approval and Consent**

It is expected that the IRB will have the proper representation and function in accordance with federally mandated regulations. The IRB should approve the consent form and protocol.

In obtaining and documenting informed consent, the investigator should comply with the applicable regulatory requirement(s), and should adhere to Good Clinical Practice (GCP) and to ethical principles that have their origin in the Declaration of Helsinki.

Before recruitment and enrollment onto this study, the patient will be given a full explanation of the study and will be given the opportunity to review the consent form. Each consent form must include all the relevant elements currently required by the FDA Regulations and local or state regulations. Once this essential information has been provided to the patient and the investigator is assured that the patient understands the implications of participating in the study, the patient will be asked to give consent to participate in the study by signing an IRB-approved consent form.

Prior to a patient's participation in the trial, the written informed consent form should be signed and personally dated by the patient and by the person who conducted the informed consent discussion.

## **8.2 Required Documentation**

Before the study can be initiated at any site, the following documentation must be provided to the Clinical Protocol Office (CPO) at the University of North Carolina.

- A copy of the official IRB approval letter for the protocol and informed consent
- CVs and medical licensure for the principal investigator and any associate investigators who will be involved in the study
- A copy of the IRB-approved consent form

## **8.3 Registration Procedures**

A list of all enrolled patients will be maintained in OnCore by the study coordinators at the University of North Carolina at Chapel Hill. Upon enrollment, affiliate sites should send UNC a copy of the signed informed consent and HIPAA documents, signed eligibility checklist, and baseline/screening questionnaire. Additional patient information may also be requested by the UNC coordinator to complete registration. For the randomized group, eligibility criteria must be confirmed with the UNC study coordinator before the start of treatment. For the observational group, eligibility must be confirmed with the UNC coordinator within 5 days of treatment start.

## **8.4 Adherence to the Protocol**

Except for an emergency situation in which proper care for the protection, safety, and well-being of the study patient requires alternative treatment, the study shall be conducted exactly as described in the approved protocol.

### **8.4.1 Emergency Modifications**

UNC and Affiliate investigators may implement a deviation from, or a change of, the protocol to eliminate an immediate hazard(s) to trial subjects without prior UNC IRB approval.

For any such emergency modification implemented, a UNC IRB modification form must be completed by UNC Research Personnel within five (5) business days of making the change. Affiliate site for this study are relying on UNC's IRB and should follow the same procedures for emergency modifications.

### **8.4.2 Single Patient/Subject Exceptions**

Any request to enroll a single subject who does not meet all the eligibility criteria of this study requires the approval of the UNC Principal Investigator and the UNC IRB.

### **8.4.3 Other Protocol Deviations/Violations**

According to UNC's IRB, a protocol deviation is any unplanned variance from an IRB approved protocol that:

- Is generally noted or recognized after it occurs
- Has no substantive effect on the risks to research participants
- Has no substantive effect on the scientific integrity of the research plan or the value of the data collected
- Did not result from willful or knowing misconduct on the part of the investigator(s).

An unplanned protocol variance is considered a violation if the variance meets any of the following criteria:

- Has harmed or increased the risk of harm to one or more research participants.
- Has damaged the scientific integrity of the data collected for the study.
- Results from willful or knowing misconduct on the part of the investigator(s).
- Demonstrates serious or continuing noncompliance with federal regulations, State laws, or University policies.

If a deviation or violation occurs please follow the guidelines below:

**Protocol Deviations:** UNC personnel will record the deviation in OnCore® (or other appropriate database set up for the study), and report to any sponsor or data and safety monitoring committee in accordance with their policies. Deviations should be summarized and reported to the IRB at the time of continuing review.

**Protocol Violations:** Violations should be reported by UNC personnel within one (1) week of the investigator becoming aware of the event using the same IRB online mechanism used to report UPIRSO.

**Unanticipated Problems Involving Risks to Subjects or Others (UPIRSO):** Any events that meet the criteria for "Unanticipated Problems" as defined by UNC's IRB (see section 0) must be reported by the Study Coordinator using the IRB's web-based reporting system.

